### Example 2:

If patient has 34 days between V3 to V4-1 and takes 34 ZOF but only 30 AML, then adherence is

- ZOF = 100\*(34/34) = 100
- AML = 100\*(30/34) = 88.24
- Total = (100+88.24) / 2 = 94.12

#### Example 3:

If patient has 14 days between V2 to V3-1 and takes 10 ZOF and 16 AML, then adherence is

- ZOF = 100\*(10/14) = 71.43
- AML = 100\*(16/14) = 114.29
- Total = (71.43+114.29) / 2 = 92.86

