#### 8.1.4.2 Derived Adherence

To ensure accuracy of adherence reported in the eCRF, adherence will also be derived directly for each patient at Visits 2, 3, and 4 as outlined below.

Treatment adherence = 100\*(actual dose/planned dose)

Actual dose = tablets dispensed at previous visit – tablets returned at current visit.

• If a subject fails to return IP, then we assume that all IP was used and return amount will be imputed as 0 tablets. This errs on the side of safety, ensuring that subject data is included in the safety analyses and that AEs are classified as treatment-emergent if they occur after dispensation of IP.

Planned dose is 1 dose per day, for the number of days between:

- V1 to V2-1 (monotherapy period approx. 28 days)
  - 1 dose = 1 tablet
- V2 to V3-1 (combined period 30/5 approx. 28 days)
  - 1 dose = 1 tablet of each assigned therapy (2 tablets total per dose)
- V3 to V4-1 (combined period 30/5 or 30/10 approx. 28 days)
  - 1 dose = 1 tablet of each assigned therapy (2 tablets total per dose)

For monotherapy period, adherence will be derived for each individual medication.

For combined therapy periods, adherence will be derived for each individual medication and then those individual adherence values will be averaged to get an overall adherence %.

Example 1:

If a patient has 28 days between V1 to V2-1, and takes 29 ZOF, then adherence is

• ZOF = 100\*(29/28) = 103.57

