#### Table 14.2.3.4 Proportion of Patients with 80% - 120% Adherence to Treatment at Visits 2, 3, and 4 (Full Analysis Set and Efficacy Population)

			All Pati (N=x	ents x)
Therapy Type	Visit	Statistic [1,2]	eCRF-Reported Adherence	Derived Adherence
Monotherapy	Visit 2	n/N (Proportion %)	xx/xx (xx.x)	xx/xx (xx.x)
		95% CI	(xx.x, xx.x)	(xx.x, xx.x)
Combined Therapy	Visit 3	n/N (Proportion %)	xx/xx (xx.x)	xx/xx (xx.x)
		95% CI	(xx.x, xx.x)	(xx.x, xx.x)
	Visit 4	n/N (Proportion %)	xx/xx (xx.x)	xx/xx (xx.x)
		95% CI	(xx.x, xx.x)	(xx.x, xx.x)

Note: The Monotherapy analysis (Visit 2) is performed on the Full Analysis Set. The Combined Therapy analysis (Visits 3 and 4) are performed on the Efficacy Population.

[1] n = number of patients who met 80% - 120% adherence to treatment at that visit. N = number of patients with data at that visit, regardless of treatment adherence status.

[2] CI = Confidence Interval.

Source: Listing 16.2.5.1

Program Name: XXXX.SAS

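### Averaging the two drugs' derived adherence lets surplus or unreturned tablets of one offset missed tablets of the other in endpoint 2.4

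*SAP*

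**What the plan says.** Endpoint 2.4 (SAP 3.2.2 and 7.3.2) is doses taken as a percentage of doses to be taken, reported at Visits 2, 3 and 4 with a 95% binomial confidence interval. A patient is compliant from 80% to 120%.

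SAP 8.1.4.2 adds an adherence figure derived from tablet counts, as a check on the value reported in the eCRF. For the combined periods it defines the planned unit as "1 dose = 1 tablet of each assigned therapy (2 tablets total per dose"). It derives a percentage for each drug, after which "those individual adherence values will be averaged to get an overall adherence" percentage. If study drug is not returned, the returned count is set to 0, so the whole box counts as taken. The reason given for that imputation concerns the safety analyses.

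Example 3 reads "If patient has 14 days between V2 to V3-1 and takes 10 ZOF and 16 AML, then adherence is" 71.43% for zofenopril and 114.29% for amlodipine, and concludes "Total = (71.43+114.29) / 2 = 92.86".

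In Table 14.2.3.4 each visit has one eCRF-reported column and one Derived Adherence column. The footnote defines the numerator: "n = number of patients who met 80% - 120% adherence to treatment at that visit". Neither the SAP text nor the table shells require each drug to be in range.

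**The concern.** The trial is about what the two drugs do together. A reader of endpoint 2.4 at Visits 3 and 4 will take the derived proportion to be the share of patients who took both drugs as planned. A mean of two percentages does not measure that, because a high value for one drug makes up for a low value for the other.

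The mean also sits badly with the SAP's own unit of dose. If a dose is one tablet of each therapy, surplus amlodipine cannot complete a dose from which zofenopril is missing. At stake is the derived proportion for one secondary endpoint, and the value of that column as a check on the eCRF figure.

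**Working it through.** **Inputs.** Formula, dose unit, averaging rule and non-return rule: SAP 8.1.4.2. Box size of 42 tablets per drug: SAP 8.1.1 and 8.1.3. Band of 80-120%: SAP 7.3.2. Interval between visits of 4 weeks ± 2 days, so 26 to 30 days: SAP 4.1.

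**1. Reproducing Example 3.** Per-drug adherence = 100 × tablets taken / days.
- Zofenopril: 100 × 10/14 = 71.43% (below 80%)
- Amlodipine: 100 × 16/14 = 114.29% (in range)
- Mean: (71.43 + 114.29)/2 = 92.86% (in range)

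The SAP's arithmetic is right. Both drugs share a denominator, so the mean equals pooled tablets: 26/28 = 92.86%. With a per-drug requirement the same patient is out of range. On the SAP's dose unit, 10 zofenopril tablets allow at most 10 complete doses of 14, or 71.43%. The 14-day interval in the example is outside the visit window, but the result does not depend on it.

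**2. How little of one drug still passes.** The table gives the smallest whole-tablet intake of one drug that keeps the mean at or above 80%, under three assumptions about the other drug.

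| Days | Other drug at 100% | Other drug at most 120% | Other box unreturned (42 imputed) |
|---|---|---|---|
| 26 | 16/26 = 61.5%; mean 80.8% | 11/26 = 42.3% with 31/26 = 119.2%; mean 80.8% | 0/26 = 0% with 42/26 = 161.5%; mean 80.8% |
| 28 | 17/28 = 60.7%; mean 80.4% | 12/28 = 42.9% with 33/28 = 117.9%; mean 80.4% | 3/28 = 10.7% with 42/28 = 150%; mean 80.4% |
| 30 | 18/30 = 60.0%; mean 80.0% | 12/30 = 40.0% with 36/30 = 120%; mean 80.0% | 6/30 = 20.0% with 42/30 = 140%; mean 80.0% |

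The first column involves no over-use at all. The third depends on the non-return imputation.

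**3. A side effect of the imputation.** At 28 days with one box unreturned, a patient who took all 28 tablets of the other drug scores (150 + 100)/2 = 125% and fails. One who took 3 tablets scores 80.4% and passes.

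**4. Direction.** If both percentages lie within 80-120%, so does their mean. The converse is false, as Example 3 shows. On the same tablet counts, then, the averaged rule passes every patient whom a per-drug rule passes, and possibly others.

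**The case against.** The strongest defence is that the mean follows the plan's wording. Protocol 7.4 and SAP 7.3.2 apply the band to the required study medication as a whole, and step 1 shows that the mean is exactly pooled tablets taken over pooled tablets planned. On that reading, a per-drug rule is a stricter definition and not the correction of a departure. This stands in part: the wording supports either reading. But the SAP's dose unit of one tablet of each therapy supports the per-drug reading, and endpoint 2.4 is expressed in doses.

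It also stands that the component information is not lost. Table 14.3.5 gives mean, median and range of derived adherence per drug at Visits 3 and 4, and Listing 16.2.5.1 gives tablets dispensed and returned by drug. Those summaries do not show how many patients had both drugs in range.

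Three stronger readings are tempting, and the documents do not support them:

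- **That the derived column must exceed the eCRF column.** Table 14.3.5 shows the eCRF category once for the combination at Visits 3 and 4, and neither document says how the two drugs are combined in it. The derived figure could be above, below or equal to it. For the same reason the eCRF figure is not a clear safeguard.
- **That the per-protocol set or the primary result is affected.** SAP 5.3.4 uses reported adherence, and nothing links the derived mean to per-protocol membership or to withdrawal at Visit 3. Endpoint 2.4 carries no hypothesis test.
- **That patients in effect on one drug will commonly be counted as adherent.** The extreme cases rest mainly on an unreturned box. The two boxes are supplied sealed together, with instructions to take both tablets at the same time (Protocol 7.1). The documents give no figure for how often intake of the two drugs differs.

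**Conclusion.** The concern holds for the derived version of endpoint 2.4 at Visits 3 and 4. The averaged rule can only equal or overstate the proportion that a per-drug rule would give on the same tablet counts. For an individual patient, a pass is possible with 60.0% to 61.5% of one drug when the other is taken in full, and with 0% to 20.0% when the other box is unreturned, over intervals of 26 to 30 days. The effect on the reported proportion cannot be sized from the documents, because it depends on how often the two drugs' tablet counts differ.

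The conclusion rests on one inference: that the averaged total is what is compared with 80-120%. No SAP sentence says so, but Table 14.2.3.4 has a single Derived Adherence column and the SAP defines no other overall derived value for the combined periods. The consequence is confined to that reported secondary proportion. The change is still worth making because it is cheap and the SAP's own example displays the problem.

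**What to change.** In SAP 8.1.4.2 and Table 14.2.3.4:

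1. For the combined periods, count a patient as within range on derived adherence only if each drug is within 80-120%. Keep the mean as a descriptive statistic in Table 14.3.5.
2. For endpoint 2.4, show unreturned boxes separately, or treat that drug's adherence as unknown, instead of imputing full use. Without this step, the per-drug rule would fail a patient with one unreturned box because of the imputation (42/28 = 150%) and not because of known intake. The imputation can stay for the safety purpose it was written for.

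Per-drug values are already derived, so the first change needs one sentence and one flag, and the second a short rule and a table row. No new data are needed, and only an analysis classification changes. The costs are a derived adherent proportion that may be somewhat lower and a derived column no longer built the same way as the single eCRF category beside it, which a table footnote should state.

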### 8.2 Adverse Events, Adverse Drug Reactions, and Deaths

Adverse Events (AEs) are any untoward medical occurrence in a clinical trial patient administered a medicinal product and which does not necessarily have a causal relationship with this treatment.

*Treatment Emergent AEs (TEAEs)* are defined as AEs that occur only once treatment has started (after the first dose of monotherapy of ZOF or AML). Thus, all AEs that occur in both the monotherapy and combined therapy periods will be considered treatment-emergent.

Adverse Drug Reactions (ADRs) are defined as AEs that have a relationship of "certain," "probable," "possible," or "unassessable."

All AEs will be coded using the Medical Dictionary for Regulatory Activities (MedDRA) version 24.1 or later.

The following tabulations will be produced for the monotherapy period and the combination therapy periods for the SAF population:

- Monotherapy Period (Day of Visit 1 through day before Day of Visit 2)
  - All treatment-emergent AEs (TEAEs)

- Severe TEAEs
- Adverse Drug Reactions (ADRs)
- TEAEs leading to study discontinuation
- Serious TEAEs (TESAEs)
- o Serious ADRs
- TESAEs with outcome of death
- Combination Therapy Period (Day of Visit 2 through Day of Visit 4)
  - All treatment-emergent AEs (TEAEs)
  - Severe TEAEs
  - Adverse Drug Reactions (ADRs)
  - TEAEs leading to study discontinuation
  - Serious TEAEs (TESAEs)
  - Serious ADRs
  - TESAEs with outcome of death

Key guidelines for counting incidence proportions of AEs/TEAEs/ADRs (collectively referred to as AEs for the remainder of this section) are as follows:

- When a patient has the same AE reported multiple times during an analysis period based on MedDRA terminology (SOC or PT), the patient will only be counted once within a level of MedDRA in an AE incidence table.
- When assessing investigator reported relationship to study drug of the AEs, if an AE reported multiple times changes in causal relationship during an analysis period for a patient, the event with highest relatedness will be presented. Related AEs (i.e., ADRs) will include those reported as "certain," "probable," "possible," or "unassessable" by the investigator.
- When summarizing severity of the AEs (mild, moderate, severe), if there are multiple AEs of the same preferred term but different severity during an analysis period for a patient, the AE with the maximum severity will be reported. If the AE term (SOC and PT) is reported more than once, one of them with missing severity, and at least another with non-missing severity, the maximum severity will be chosen from the non-missing severity and the missing severity can be ignored. If all are of missing severity, then the AE severity will be summarized with an additional "Missing" category. In summary of severe AEs, missing severity will be included in severe category following the conservative approach.

All AE tabulations for the monotherapy period will present the incidences separately for the monotherapy groups (ZOF 30 mg or AML 5 mg) and All Patients for the SAF population. That is, all patients who experienced at least one AE in the monotherapy period will be summarized together in the All Patients column of the corresponding summary tables. All patients who take ZOF 30 mg will be summarized in the ZOF 30 mg column and all patients who take AML 5 mg will be summarized in the AML 5 mg column.

All AE tabulations for the combined therapy period will present the incidences separately for the combined treatment groups (ZOF/AML 30/5 mg or ZOF/AML 30/10 mg) and All Patients for the SAF population. That is, all patients who experienced at least one AE in the combined therapy period will be summarized together in the All Patients column of the corresponding summary tables. All patients who take ZOF/AML 30/10 mg will be summarized in the ZOF/AML 30/10 mg column, even for AEs that occurred while taking the ZOF/AML 30/5 regimen. Lastly, all patients who take ZOF/AML 30/5 mg for the duration of the combined therapy period will be summarized in the ZOF/AML 5 mg column.

In summaries by SOC and PT (for both monotherapy and combined therapy periods), AEs will be sorted by descending frequency for SOC and PT in the All Patients column. All AEs will also be presented in bypatient data listings for Adverse Events for the SAF population.

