8.2 Assessment of Safety

Safety will be assessed through collection of treatment-emergent AEs, serious AEs (SAE), , that started after the first dose of study treatments (incidence, severity, seriousness, treatment causality), and physical examination (, vital signs, BP, and heart rate). Safety assessments will be performed at time points as described in Section 9.

МЕМАЯМ	Corporate Medical Department		
Identification Number	Version Number	State	Effective date
FORM-000050125	2.0, CURRENT	Effective	08, Jan 2021

Urine Pregnancy test

Study medication should not be given to pregnant female. Therefore, Urine Pregnancy tests will be performed in all females of childbearing potential at Screening and each subsequent visit during the study.

Physical examination

The Investigator (or site staff) must perform a complete physical examination at Screening and each subsequent visit during the study. At the Screening visit height, weight (in indoor clothing but without shoes) and body mass index [BMI] calculation will be recorded. At all visits, the physical examination will include general appearance, skin, head, neck, ear-nose-throat (ENT), heart, lungs, abdomen, extremities, neurological, musculoskeletal and lymph nodes. Information pertaining to physical examinations must be included in the source documentation at the study site. Any new finding, or worsening of a previous finding, should be reported as a new AE.

Vital Signs

Body temperature (°C) and heart rate will be measured under the same conditions at Screening and all subsequent visits (Visit 2, Visit 3, and Visit 4). If possible, vital sign assessment should be performed by the same study site staff member using the same validated device throughout the study. Blood pressure will also be measured at all visits as described above. Vital signs should be performed prior to taking the blood samples.

Electrocardiograms

In this study, Local ECG will be used and will be performed by a qualified clinical site physician. All 12-lead electrocardiogram (ECG) will be standardized recordings. Single 12-lead ECGs will be performed at Screening (Visit 1) and at Visit 4. Additional 12-lead ECG will be performed at other times if judged to be clinically appropriate or if the on-going review of the data suggests a more detailed assessment of ECG is required. ECGs will be performed in triplicate at Visit 1 and Visit 4.

МЕМАЯМ	Corporate Medical Department		
Identification Number	Version Number	State	Effective date

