9.9 Collection, Recording and Reporting of AEs

At each visit the Investigator will collect and assess any occurred subjective or objective AE occurred to each subject after his / her signature of the informed consent.

The Investigator should manage as AE any laboratory test abnormality (newly occurring after the IMP administration or worsening of previously known abnormalities) considered as clinically relevant: i.e. values significantly above or under normal range or which require an intervention or diagnostic tests, or may result in the IMP discontinuation.

Any AE communicated by the subject or by the subject's relatives or delegates through phone calls, letters or e-mails will also be collected and assessed.

The Investigator shall record on the respective eCRF AE recording pages / AE form any recognised AE identifying an ICSR, both serious and non-serious, whether or not thought to be drug-related, observed in or reported by the subject (or relatives / delegates), specifying the judgement on the causal relationship with the study treatment.

Any available information and diagnostic measure (laboratory and instrumental tests, procedures, etc.) shall be recorded in and / or attached to the concerned eCRF pages / sections.

HENYBINI	Corporate Medical Department		
Identification Number	Version Number	State	Effective date
FORM-000050125	2.0, CURRENT	Effective	08, Jan 2021

The Investigator is expected to also record any AE which was ongoing at the last treatment dose and a follow-up phone call should be made after 2 weeks from the last study visit. The Investigator is expected to follow up any AE occurred during the study, including the follow-up period, until the outcome of the AE has been determined.

The Investigator must report all the collected information on any ICSR with Serious and Non Serious AE (whether or not thought to be related to the investigational drug), providing the *concerned eCRF-AE pages/ by alert email*), after the first knowledge of the occurrence of the case, to:

CRO Pharmacovigilance Officer:

Email: MEIN/20/ZoAm-Hyp/[contact]

[contact] [contact]

Mobile: N/A

When relevant, also the eCRF pages concerning medical history, concomitant medication, and laboratory tests will be placed at Sponsor disposal by email.

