### 5.6.2 Imputation of Adverse Event Start Dates

Partial start dates for Adverse Events (AEs) are imputed as detailed below in order to classify each AE as treatment-emergent, as defined in section 8.2.

Start date:

- If start date is completely missing, start date is set to date of first dose.
- If (1) year is present and month and day are missing or (2) year and day are present and month is missing:
  - If year = year of first dose, then set month and day to month and day of first dose.
  - If year < year of first dose, then set month and day to December 31st.
  - If year > year of first dose, then set month and day to January 1st.
- If month and year are present and day is missing:

- If year = year of first dose and
  - If month = month of first dose, then set day to day of first dose date.
  - If month < month of first dose, then set day to last day of month.
  - If month > month of first dose, then set day to 1st day of month.
- If year < year of first dose, then set day to last day of month.
- If year > year of first dose, then set day to 1st day of month.

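### SAP 8.2 has no worsening clause, so a run-in adverse event that worsens on the combination may be absent from the combination tables and be tabulated under monotherapy

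*SAP*

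**What the plan says.** SAP 8.2 says that treatment-emergent adverse events "are defined as AEs that occur only once treatment has started (after the first dose of monotherapy of ZOF or AML". The same set of tables (all events, severe, drug reactions, leading to discontinuation, serious, serious reactions, fatal) is then produced for two windows: "Monotherapy Period (Day of Visit 1 through day before Day of Visit 2" and "Combination Therapy Period (Day of Visit 2 through Day of Visit 4". Neither the definition nor the list of tables mentions an event that worsens.

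On severity, SAP 8.2 says that when a patient has several events of one preferred term at different grades within an analysis period, "the AE with the maximum severity will be reported".

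Two other places tie emergence to onset. Protocol 8.2 describes the events assessed as those "that started after the first dose of study treatments (incidence, severity, seriousness, treatment causality". SAP 5.6.2 says: "Partial start dates for Adverse Events (AEs) are imputed as detailed below in order to classify each AE as treatment-emergent".

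The Protocol addresses worsening in two places. Under physical examination in section 8.2: "Any new finding, or worsening of a previous finding, should be reported as a new AE". In section 9.9, a clinically relevant laboratory abnormality is managed as an AE if it is "newly occurring after the IMP administration or worsening of previously known abnormalities".

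**The concern.** Endpoint 2.5 asks for tolerability of the monotherapies and of the combination separately, so the division at Visit 2 is what gives these tables their meaning. Under Protocol section 5, patients enter the assessment period only if the run-in treatment was well tolerated. If an entrant's continuing run-in symptom later becomes severe, becomes serious or leads to withdrawal, that happened on two drugs.

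In a patient who already has a symptom on one drug, poor tolerance of the second may show as worsening of the existing event and not as a new one. A rule that looks only at when the event began would put that worsening in the wrong period: the combination tables would look better than they should and the monotherapy tables worse. It would also treat like cases differently. Worsening found on examination would count under the combination, while worsening reported as a symptom might count under monotherapy.

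**Working it through.** No arithmetic applies. The check sets the provisions side by side and follows an event through them.

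**1. Is period set by start date?** SAP 8.2 does not say so outright. The supporting evidence is:
- Protocol 8.2 and SAP 5.6.2 both key on the start of the event.
- SAP 5.2.2 defines first dose as the first combination dose. Comparing a partial start date with first dose, as SAP 5.6.2 does, therefore sorts events around Visit 2.
- Listing 16.2.7.1 carries one start date and one therapy-period flag (M or C) per AE number.

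Together these make start-date assignment the natural reading.

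**2. Can the data show when an event changed?** Listing 16.2.7.2 carries severity, relationship, outcome, action taken and study discontinuation for each AE number, with no date of change. The seriousness field in Listing 16.2.7.1 has none either.

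**3. Does the maximum-severity rule help?** It works within one analysis period, across several events of the same preferred term. It does not reach a single record that runs across Visit 2.

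**4. Does the Protocol require a new record on worsening?** It does for examination findings. Clinically relevant laboratory worsening is managed as an AE. For other events, section 9.9 asks for follow-up until the outcome is known and gives no instruction to open a new record when grade or seriousness changes.

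**5. Following the cases through:**

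| Event | Where it is counted |
|---|---|
| Run-in examination finding that worsens after Visit 2 | Combination, as a new AE |
| Clinically relevant laboratory worsening, given its own date after Visit 2 | Combination (laboratory tests are scheduled at Visits 1 and 4 only) |
| Run-in symptom, ECG or vital-sign AE that worsens after Visit 2, site opens a new record | Combination |
| Same, kept as one record, period by start date | Absent from combination; if updated to its worst grade, severe or serious under monotherapy |
| Same, kept as one record, ongoing events counted in both periods | Both periods, with the worst grade shown in each |
| Event starting on 30/5 after Visit 2 that worsens on 30/10 | Combination, in the 30/10 column |

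The fourth row is the defect. ECGs are scheduled only at Visits 1 and 4, so symptoms are the main route into it.

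**The case against.** The strongest reply is that start-date assignment is inferred. SAP 8.2 speaks of events that occur, and of patients who experienced an AE, in the combined therapy period, so an event ongoing at Visit 2 could be counted there. That is a fair reading of the words, but it does not repair the tables. An unchanged run-in symptom would then be charged to the combination, and a single record at its worst grade would still appear under monotherapy.

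The second reply is that SAP 8.2 foresees repeated records with differing severity or causality. If sites open a new record at each change, the allocation is right. This stands as a possibility. Record-keeping is left to the eCRF user guidelines (Protocol 15.2), which are not among the documents. It is the reason the conclusion says may and not will.

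Third, other outputs show part of the picture. Table 14.1.1 gives discontinuation for adverse events by combination column, and its row for exclusion at Visit 3 includes intolerance. Examination shift tables run from Visit 2 to Visits 3 and 4. All AEs are in by-patient listings. The Visit 2 tolerability requirement also reduces the number of entrants with troublesome run-in symptoms. All of this stands and limits the consequence, but none of it corrects the AE tables by period.

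A reader might infer that worsening is never counted, that affected events vanish from the report, or that worsening after the amlodipine increase is generally missed. The documents support none of these. Examination and laboratory worsening are provided for, the listings keep every event, and an event with onset after Visit 2 stays in the combination tables at either dose.

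**Conclusion.** The gap is real but narrow. It concerns symptom, ECG and vital-sign AEs that start in the run-in, are ongoing at Visit 2, and then increase in severity, become serious or lead to discontinuation on the combination. Such an event may be missing from the combination tables. If it is one record at its worst grade, it may stand as a severe or serious monotherapy event.

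The conclusion rests on two assumptions: that period follows start date, which is well supported but not stated, and that the site keeps a single record, which cannot be checked here.

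The size cannot be estimated, because the documents give no AE rates, no proportion ongoing at Visit 2 and no rate of worsening. Any figure for worsening of all grades would also overstate the effect on the severe and serious rows. If counts in those rows are small, one or two misplaced patients could change what they show. The affected tables are descriptive, and the primary endpoint is untouched. The rule should be settled before database lock.

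**What to change.** In SAP 8.2, state that period follows the start date of each AE record. Add that an AE which increases in severity or becomes serious on or after the first combination dose is treatment-emergent in the combination period.

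The SAP sentence alone cannot be programmed for single records, because the AE listings show no date of change. So extend the Protocol's existing instruction for examination findings to all AE types, for example in the eCRF guidelines: each increase in severity or change to serious gets its own record with its own start date and grade. Before database lock, query single-record AEs that were ongoing at Visit 2.

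A run-in event that leads to discontinuation after Visit 2 at an unchanged grade would not be caught by this clause. The SAP should say which period's discontinuation table takes it; Listing 16.2.1 already holds the date of study discontinuation.

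The cost is a short SAP addition, an eCRF completion note, some extra site queries and slightly higher AE counts on the combination. The primary endpoint and its analysis do not change.
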